3.1.3 Data collection

Information on exposures (depression status, and treatment), outcome (PTD & LBW), and other psychiatric disorders (comorbidity) will be ascertained through KPNC EMR data sources for all

88,000 women who have been screened for peripartum depression. Confounders not available from the KPNC EMR will be ascertained during interview of the stage-two subsample of 3,600 women (Figure 2). OBGYNS will inform all pregnant women who screen positive by PHQ-9 about our study during their prenatal visits. Table 1 describes briefly the sources and categories of factors to be ascertained.

		Universal Screening	EMR data	Interview
Depression and treatment	Depression and its severity	X	X	
	Psychotherapies	X	X	
	Antidepressant use	X	X	
	Combination therapy	X	X	
	Other psychiatric disorders		X	
Outcome	Gestational Age/PTD, LBW		X	
Potential confounders, mediators and effect modifiers	Risk factors for PTD, LBW		X	X
	History of mental illness		X	X
	Reproductive history		X	X
	Preexisting diabetes or GDM		X	X
	BMI		X	X
	History of depression	X	X	X
	Substance abuse		X	X
	Reproductive and pregnancy history		X	X
	Family and social support		X	X
	Demographic characteristics		X	X
Family history of mental illness			X	

Depression status and severity

Depression status and its severity during pregnancy will be ascertained through PHQ-9 scores from the universal depression screening and clinical diagnosis. All pregnant women who come to the first prenatal visit will be screened for depression using the PHQ-9, which has been validated in many studies as an instrument for screening for depression with high sensitivity (> 88%) and specificity (> 88%) in obstetric patients¹⁰³⁻¹⁰⁷. PHQ-9 was chosen as the screening instrument after consultation with many nationally recognized experts in the field of diagnosis and treatment of peripartum depression balancing out many factors including scientific validity and feasibility for a large scale population-based screening program. As a currently accepted cutoff, PHQ-9 scores (≥ 10) in combination with evaluation by medical practitioners will be used to determine whether a pregnant woman screens positive for depression. A score above 10 will be used as a measure of the severity of depression. Women who screen positive are referred by clinicians, under the screening protocol, to departments of

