psychiatry, psychology, or behavioral modification. Information on PHQ-9 scores, referrals, patient's uptake (or decline) of prescribed treatments are also captured by our EMRs. Any clinical diagnosis and treatment of depression for those not captured by the screening will also be identified through EMRs. During the glucola visit (22-24 weeks of gestation), all women will be screened for depression a second time using the same screening process as the first prenatal visit.

Women being treated for depression before the screening will be identified (<2%) and analyzed as a separate group.

Depression severity will also be used for stratification (to control for confounding by indication) when conducting head-to-head comparison of treatment effect among various treatment options.

Depression type (with or without other psychiatric comorbidity) will be determined by identifying concurrent psychiatric disorders from KPNC EMRs including organic psychotic conditions, other psychoses, neurotic and personality disorder and other mental disorders. The expected number of women who have depression only and depression with comorbidity during the study period is listed in Figure 2.

Antidepressant use during pregnancy. Antidepressant use, including types, timing, and duration of use, will be ascertained both through the depression screening and EMR (i.e., pharmacy database). The KPNC pharmacy database captures all inpatient and outpatient prescriptions and dispensations. Because of a large financial incentive to obtain medications at KPNC (in most cases, medications are covered with minimal co-payments), the KPNC pharmacy database has been shown to capture 93-98% of prescription medications of varying types. Compliance of taking antidepressants will also be ascertained during interview.

Psychotherapy. KPNC EMR records any psychotherapy patients receive for depression. The information includes the type of therapies (individual or group), sources of the treatment (psychologist, behavioral modification specialist, or psychologist/social worker) and number of sessions attended.

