5 COMPARATORS

Comparators will vary depending on the research questions to be examined in analyses. The overall objective is to use appropriate comparators so that correct results of comparative effectiveness can be obtained after disentangling treatment effect from the effect of underlying depression (confounding by indication), and treatment benefits after balancing treatment benefit against the simultaneous risk of side effect (e.g., use of antidepressants). The following four cohorts (A-D) will be established within each depression type (depression only or depression with comorbidity) and various comparators will be used to answer the research questions in the Specific

Aims. We will also establish a control cohort (E) of women without depression for comparison of baseline risk.

Cohort A: women who screened positive and used antidepressants only. All women who screened positive for depression and were subsequently prescribed antidepressants during pregnancy will form Cohort A. Comparison of this cohort to Cohort D, a comparator for Specific Aim 1, will demonstrate the treatment effect of antidepressant use in reducing the fetal risk after controlling for severity of depressive symptoms and other confounders. Comparisons to Cohort B or C, comparators for Specific Aim 2, will determine which treatment option (antidepressant use, psychotherapy or combination therapy) is more effective in reducing fetal risk or has a better risk-benefit profile (pair-wise comparisons). Results from such comparisons will provide valuable information for clinicians as well as pregnant women to make an informed decision on the treatment options for depression during pregnancy based on research evidence.

Cohort B: women who screened positive and received psychotherapy only. This cohort consists of women who screened positive and subsequently received psychotherapy during pregnancy, but did not take any antidepressants. Comparison to Cohort D will determine if mitigation of depression by psychotherapy reduces fetal risk, after controlling for depression severity. Comparisons of this cohort to antidepressant use (Cohort A) or combination therapy (Cohort C), two separate comparators for Specific Aim 2, will provide head-to-head assessment of comparative effectiveness of treatment regimens.

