Cohort C: women who screened positive and used both antidepressants and psychotherapy. This will be a cohort similar to Cohort A and B except that women in this cohort received combination therapies after screening positive. We classify them in a separate cohort to make Cohorts A and B encompass more clearly defined exposures of antidepressants and psychotherapy (pure exposure groups). In addition, this cohort may allow us to examine the potential benefit of combination therapy. Like Cohorts A and B described above, they will be compared to untreated comparator (Cohort D) for Specific Aim 1 and other treatment comparators (Cohort A and B) for Specific Aim 2.

Cohort D: women who screened positive for depression, and did not obtain treatment. Pregnant women whose PHQ-9 score is ≥ 10 at either of two screening visits (the first prenatal visit and glucola visit) or who were diagnosed as having depression by their medical providers, but did not receive any treatment for depression during pregnancy, will be classified into this cohort. Comparison of this cohort to Cohort E (control cohort), a comparator for Specific Aim 3, will allow us to assess whether untreated depression during pregnancy increases fetal risk (i.e., PTD or LBW) without the interference of treatment effect. We can also examine potential dose-response relationships based on the severity of depression (PHQ-9 scores) and duration of depression (persistence of the symptoms in both screening visits vs. at only one of the visits). Importantly, this cohort can be used as a comparator for Cohorts A, B, and C to examine the effect of depression treatment after controlling for underlying depression and severity (untreated comparators).

Cohort E (controls): women who screened negative for depression in both visits and did not receive treatments for depression. This cohort consists of the largest number of pregnant women, those who have neither depression and concurrent psychiatric comorbidity, nor treatment during pregnancy. This cohort will serve as the comparator for determining the effect of untreated depression on fetal risk (i.e., PTD, LBW). It will also serve as a reference check for other

comparisons. For example, does the benefit of a treatment totally eliminate the risk of PTD associated with depression during pregnancy?

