Aim 3. Risk of PTD & LBW for untreated depression (Cohort D vs. E)

Cox proportional hazards regression will be used to obtain point and interval estimates of the hazard ratio for PTD associated with untreated depression, vs. no depression, with adjustment for potential confounders, as described above. Parameter estimation, the approach to inclusion of potential confounders and model diagnostics are as described above for Aim 1 analyses.

To evaluate potential dose-response relationships, we will examine the strength of the association between PTD and severity of depressive symptoms. Severity will be based on results of the KPNC universal screening and clinical diagnosis of depression from the KPNC EMR. Those with a clinical diagnosis of depression will be considered to be the most severe cases followed by those who screened positive with PHQ-9 higher scores (e.g., > 20). Those who screened positive, but with lower PHQ-9 scores (10-19) will be considered to have moderate depression. The effect of severity will also be examined in terms of duration.

Analyses of LBW as the outcome will parallel those described above for PTD, but logistic regression techniques will be used rather than the Cox model.

Aim 4. Difference in treatment effectiveness by depression type (with and without comorbidity)

Analyses of Aims 1, 2 and 3, will be initially stratified by depression type, with or without other psychiatric comorbidity (yes/no). Heterogeneity in treatment effectiveness by depression type will be assessed by inclusion of appropriate cross-product (interaction) terms in regression models outlined above, using a likelihood ratio test. If there is evidence of heterogeneity, point and interval estimates of relative hazards/odds ratios of interest by comorbidity status (yes/no), adjusted for confounders, will be obtained via linear combination of regression parameter estimates (main effect and interaction terms, as appropriate).

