6.2 Avoidance of bias

The most important strength of the proposed study is the existence of the unique KPNC region-wide universal peripartum depression screening program. Such a universal screening provides a rare opportunity to conduct a large scale (N= 88,000) population-based comparative effectiveness study of depression treatment on reducing fetal risk, while avoiding potential selection bias. Without such a screening program, a large percentage of pregnant women with depression (>50%) would not have been identified, since depression during pregnancy is

substantially under-recognized and under-diagnosed^{5, 14, 45}. Thus, relying solely on clinical diagnosis of depression would likely lead to self-selection bias.

Given that randomized clinical trials are not feasible for evaluating treatment effectiveness on reducing fetal risk due to ethical concerns about assigning women into a treatment group with potential fetal risk, the proposed two-stage prospective cohort study is likely one of the best alternatives to examine the comparative effectiveness of treating depression during pregnancy. In addition to significantly reducing self-selection bias, the results of universal screening will provide information on depression severity measured by PHQ-9 score for participants. This valuable information will allow us to control for not only depression (yes/no), but also depression severity (a continuous scale) at baseline. While the distribution of depression severity was comparable among treatment groups (Table 2), ability to control for confounding by indication in such a refined detail will substantially increase the validity of our findings. Such a refined control for baseline depression severity is not likely feasible in other settings without universal peripartum depression screening.

We have also implemented several analytic methods to address the issue of possible selection into various treatment groups including *propensity score* analysis for balancing unobserved factors among treatment group and *instrument variable* analysis for possible unmeasured confounders (see Analytic Methods).

Finally, the findings from this observational study based on real world clinical experience is more relevant and applicable to actual clinical practice compared to findings from much controlled settings with selected populations (RCTs).

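### Depression type comes from psychiatric diagnoses in the medical record with no pre-treatment cut-off, so the stratum used in Aims 1 to 4 can partly result from treatment

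*Combined protocol and SAP*

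**What the plan says.** Depression itself is found by PHQ-9 screening of every woman at two visits, together with clinical diagnosis (Section 3.1.3). Depression type is handled differently: "Depression type (with or without other psychiatric comorbidity) will be determined by identifying concurrent psychiatric disorders from KPNC EMRs". The same section says that "other psychiatric disorders (comorbidity) will be ascertained through KPNC EMR data sources for all" screened women, and Table 1 marks neither screening nor interview as a source for other psychiatric disorders. No window, look-back, diagnosing setting or order relative to treatment is given. Manual record review is planned for PTD and LBW only.

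On contact with services, Section 3.1.3 says: "Women who screen positive are referred by clinicians, under the screening protocol, to departments of" psychiatry, psychology or behavioral modification. Section 5 gives the cohort rules:
- Cohorts B and C received psychotherapy by definition.
- For Cohort A, "All women who screened positive for depression and were subsequently prescribed antidepressants during pregnancy will form Cohort A".
- For Cohort D, depressed women who "did not receive any treatment for depression during pregnancy, will be classified into this cohort".

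Section 5 finalizes cohort membership at the end of pregnancy. Section 4.1.3 lets changes in depression and treatment status after first assignment be corrected at analysis.

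Depression type divides the eight depressed cohorts (Section 4.1.1) and stratifies Aims 1 to 3. It is also the modifier in Aim 4: "Heterogeneity in treatment effectiveness by depression type will be assessed by inclusion of appropriate cross-product (interaction) terms in regression models" (Section 6.1).

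**The concern.** A stratifier should be fixed before the exposure it stratifies. Here a diagnosis first recorded during psychotherapy can decide which stratum a woman is in. Take two women who are alike at a positive screen, each with an unrecorded second disorder. The one who attends therapy has more opportunity to be recorded as comorbid, while the one who declines is more likely to stay in the depression-only part of Cohort D.

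If recording is less complete in D, its depression-only stratum keeps hidden comorbid women whom the psychotherapy cohorts have moved out. Should comorbidity raise PTD or LBW risk, psychotherapy could look protective in that stratum with no true effect, and Aim 4 could pick up a difference in detection. Cohort A needs only a prescription, so A versus B or C in Aim 2 is exposed to the same problem.

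The plan sees this kind of risk for depression, where "relying solely on clinical diagnosis of depression would likely lead to self-selection bias" (Section 6.2), but does not carry the thought over to comorbidity. Its background section (A.a.6) expects the two depression types to differ in fetal impact, so misplacing women between them could matter.

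**Working it through.** **1. Plan figures that rest on this variable.** Section 6.2.2 gives minimum detectable interactions for PTD of 1.50 (N = 1,600, PTD 9.5%) and 1.31 (two-stage). This point disputes neither, but they are the natural yardstick, so they were checked with log HR = 2.80 × √(sum of 1/events over four cells).
- 400 per cell at 9.5% gives 38 events per cell: exp(2.80 × √(4/38)) = 2.48, not 1.50.
- 1,600 per cell gives 152 events per cell: exp(2.80 × √(4/152)) ≈ 1.58, not 1.31.

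The stated values did not reproduce as interactions. That is a separate matter; here it only means that 1.31 is a lenient yardstick.

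**2. Formulas for the illustration.** Let p be true comorbidity among depressed women, d the proportion of it recorded, and RR the PTD risk ratio for comorbid versus not. Assume no false comorbidity codes and no true treatment effect.
- Hidden comorbid share of the depression-only stratum: f = p(1 − d)/(1 − pd).
- Spurious ratio, treated versus D: [1 + f_T(RR − 1)]/[1 + f_D(RR − 1)].

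**3. Inputs, all assumed.** p = 30-50%, equal in every cohort; d = 90% in treated women and 50-70% in D; RR = 1.375 to 2.0. The value 1.375 is 11%/8%, the ends of the expected PTD range in Section 6.2.2. That is an overall range, used only for scale, and not a comorbidity contrast.

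| p | d in D | f_T | f_D | ratio, RR 1.375 | ratio, RR 2.0 |
|---|---|---|---|---|---|
| 30% | 70% | 0.03/0.73 = 0.041 | 0.09/0.79 = 0.114 | 1.015/1.043 = 0.97 | 1.041/1.114 = 0.93 |
| 50% | 50% | 0.05/0.55 = 0.091 | 0.25/0.75 = 0.333 | 1.034/1.125 = 0.92 | 1.091/1.333 = 0.82 |

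These are the mildest and strongest combinations of p and d, so the overall range is 0.82 to 0.97. With equal recording (90% in both groups) the ratio is 1.00. If women recorded as comorbid show no such distortion, the spurious interaction is the reciprocal, about 1.03 to 1.22.

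**4. Relaxing equal true comorbidity.** Keep 50% in treated women (f_T = 0.091) and recording of 90% versus 70%.
- D at 30%: f_D = 0.114; ratios 0.992 (RR 1.375) and 0.979 (RR 2.0).
- D at 20%: f_D = 0.06/0.86 = 0.070; ratios 1.008 and 1.020, so the direction reverses.

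**5. What a look-back could leave behind.** Suppose pre-screen recording is 60% in treated women and 40% in D (assumed), with p equal at 30-50%.
- f_T = 0.12/0.82 to 0.20/0.70 = 0.15 to 0.29.
- f_D = 0.18/0.88 to 0.30/0.80 = 0.20 to 0.38.
- Ratios: 0.97 to 0.98 (RR 1.375) and 0.94 to 0.95 (RR 2.0).

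**The case against.** A reader might infer that treated and untreated women are classified by different rules, or that women in Cohort D are never clinically assessed. The documents support neither. One record-based rule applies to everyone, and the most that can be said is that its sensitivity is probably unequal. A positive screen already involves evaluation by a practitioner, Cohort D includes women whose providers diagnosed depression, and nothing says that a comorbidity code requires a mental-health visit. The Section 6.2 warning about clinical diagnosis concerns depression, not comorbidity. These objections stand.

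There is also partial mitigation. The stage-two interview asks every cohort about personal history of mental illness, whatever their contact with services. It is collected as a potential confounder, however. It enters the model only if the comparison of adjusted and unadjusted estimates favors it, and nothing in the plan lets it reassign strata. PHQ-9 adjustment addresses depression severity rather than a second disorder, and propensity scores computed within strata already formed cannot undo how they were formed.

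The size is assumed throughout, and step 4 shows that the direction is not secure. The illustrative interaction of 1.03 to 1.22 lies below even the stated 1.31, so alone it would often go undetected. It would still shift the estimates. Finally, Aim 3 (D versus E) has no treated arm. The issue there is hidden comorbidity in D, not classification caused by treatment.

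**Conclusion.** The point holds in a limited form. The stratifier for Aims 1 to 3 and the Aim 4 modifier is not fixed before treatment, and recording after the positive screen is probably more complete in Cohorts B and C than in D, or in A without mental-health contact. That follows from the referral pathway and the cohort definitions; the documents do not measure it. The comparisons exposed are B and C versus D, A versus B or C, and the interaction.

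The spurious ratio of 0.82 to 0.97 is an illustration. It depends on equal true comorbidity across cohorts, the assumed recording rates, no false codes, and a comorbidity risk ratio of 1.375 to 2.0. It would be tempting to conclude that the study will show a false benefit of treatment, or false heterogeneity by depression type. The documents do not support that, because neither size nor direction can be obtained from them. This is a cheap improvement rather than a fatal flaw.

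**What to change.** For the primary analysis, define comorbidity as a psychiatric diagnosis in the record within a fixed look-back (for example 12 months) ending at an index date before study treatment:
- Cohorts A to D: first positive PHQ-9 screen or first depression diagnosis.
- Cohort E: the first prenatal screen. E needs its own anchor because it has no positive screen, yet Section 5 requires it to be free of comorbidity.

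State that later diagnoses do not move a woman between strata, and use this rule for both the cohorts and the Aim 4 interaction. Report two sensitivity analyses: comorbidity recorded at any time in pregnancy, and a version using interview history of mental illness in stage two.

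The direct cost is an extraction rule and some protocol wording. The drawbacks are real:
- Comorbidity first recognized in pregnancy is counted as absent.
- Women new to the health plan have a shorter look-back.
- The comorbid cohorts become smaller. They should be checked against the 400 interviews needed in each; the expected counts are in Figure 2, which the reviewed copy does not show.
- Differences from earlier care-seeking remain (step 5). They precede treatment, and the small group already treated before screening (under 2%) is analyzed separately. The change therefore removes the part of the classification that treatment itself causes, but not all unequal detection.
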